5.2.1.4 We will first treat 6 patients at dose level -1 in the lead-in phase. If DLT occurs in $\geq 2/6$ patients, this dose level would exceed the MTD, and 6 patients will be treated at the next lower dose level (i.e. dose level -2). If DLT is observed in the first 28 days of treatment in 0 or 1/6 at dose level -1, then dose level 0 will be evaluated. The dose adjustment (Table 1) will continue in cohorts of 6 until we reach a dose level at which $< 2/6$ patients experience a DLT in the first 28 days. The dose level at which 0-1/6 patients experience a DLT in the first 28 days of treatment will be the MTD and will be used to treat an additional 34 patients in the phase II portion of the study. If $\geq 2/6$ patients experience DLT at dose level -4, the study will be revised to consider additional lower dose levels (based on potential synergistic toxicity).

5.2.1.5 Patients that are removed from study before day 28 for any reason other than toxicity and have not experienced DLT will be replaced.

5.2.2 One cycle of therapy is defined as 28 days. Patients will receive one cycle of therapy every 28 days (+/- 7 days).

5.2.2.1 In the phase II part of the study (once the MTD dose has been defined) cycles may be started early (but not earlier than day 21) for patients with active disease if judged in the best interest of the patient.

For the lead-in cohort, DLT defining period is 28 days. As such, cycle 2 should not be started before 28 days for the patients being treated on the lead-in cohort.

5.2.2.2 Subsequent cycles may be delayed for recovery of toxicity or other medical conditions (e.g. infections). Delays in start of subsequent cycles greater than 8 weeks will be acceptable only for patients who are deriving clinical benefit and after discussion with the principal investigator of potential risk/benefit ratio.

5.2.2.3 In instances where one drug has to be discontinued transiently because of safety, the administration of the other drug may continue as scheduled. If the drug that is held can resume at a later time, no doses will be made up and the administration will follow the originally defined schedule calendar according to the drug that was continued.

5.2.2.4 Subsequent courses of 5-azacytidine and lirilumab may be administered regardless of peripheral blood counts during the first 4 cycles and/or in the presence of residual leukemia.

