11.1 Sample Size

Part a. Lead-in phase

The primary objective of the lead-in phase is to determine the safety of lirilumab in combination with 5-azacytidine in patients with refractory/ relapsed AML. Up to 24 patients will be accrued into lead-in part of the study.

Part b. Phase II

Up to 40 patients (including 6 patients treated at the MTD from the lead-in part) will be recruited for the Phase II part.

The primary objective of the phase II is to determine the efficacy of lirilumab in combination with 5-azacytidine in patients with refractory, relapsed or untreated AML. The efficacy of the combination will be measured by the overall response rate (ORR), defined as CR (complete remission) + CRp (complete remission with incomplete platelet recovery) + CRi (complete remission with incomplete count recovery) + PR (partial response) + marrow clearance of blasts + HI (Hematological improvement) within 3 months of treatment initiation among adult patients with refractory/ relapsed AML. ORR and toxicity will be monitored simultaneously using the Bayesian approach of Thall, Simon, Estey (1995, 1996) and the extension by Thall and Sung (1998).

Once safety of the MTD has been established, any patients still on study at a dose lower than MTD can be dose escalated up to MTD. Patients treated in the lead-in phase at MTD will be included in the phase II portion of the study.

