All patients who received any dose of the study agent will be included in the analysis for efficacy and safety. Demographic/clinical characteristics (including duration of response) and safety data of the patients will be summarized using descriptive statistics such as mean, standard deviation, median and range. For the primary efficacy analysis, we will estimate the ORR for the combination treatment, along with the 95% confidence interval. Patients who drop out of the study before completing all the cycles will be treated as “failures” for the primary analysis. ORR during the study period will also be presented with the 95% confidence interval. The association between ORR and patient’s clinical characteristics will be examined by Wilcoxon’s rank sum test or Fisher’s exact test, as appropriate. Toxicity type, severity and attribution will be summarized for each patient using frequency tables.

The distribution of time-to-event endpoints (DFS and OS) including overall survival and progression free survival will be estimated using the method of Kaplan and Meier. Comparisons of time-to-event endpoints by important subgroups will be made using the log-rank tests. Paired t-tests will be used to determine the immunological and molecular changes in the peripheral blood and bone marrow from baseline to the time of response, and to the time of disease progression. Correlation analysis (such as logistic regression analysis) will be conducted to determine the relationship between induction of hypomethylation / DNA damage and clinical response.

Statistical analysis of biomarker data: Descriptive statistics including plots, mean, median and standard deviations will be used to summarize data. For continuous outcomes, t-test and ANOVA will be used to compare outcome measures across patient characteristics. Dunnett’s and Tukey’s test that properly adjust for multiplicity in multiple tests will be implemented. Pair-wise comparisons will be performed using pre- and post-therapy samples from each patient . The chi-square test or Fisher’s exact test will be used to test the association between two categorical variables such as disease state and performance status. Both univariate and multivariate logistic regressions will be performed to model prognostic factors.

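### The efficacy set in section 11.2 (anyone given any dose) conflicts with the phase II cohort of 40 treated at the MTD in sections 11.1 and 5.2.1.4, so the primary ORR denominator is not fixed

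*Combined protocol and SAP*

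**What the plan says.** Four places in the combined protocol and SAP bear on who is counted in the ORR.

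- Section 11.2, analysis paragraph: "All patients who received any dose of the study agent will be included in the analysis for efficacy and safety". The primary analysis follows: "For the primary efficacy analysis, we will estimate the ORR for the combination treatment, along with the 95% confidence interval". Neither sentence names a dose level or a part of the study.
- Section 11.1: "Up to 40 patients (including 6 patients treated at the MTD from the lead-in part) will be recruited for the Phase II part". On carry-over: "Patients treated in the lead-in phase at MTD will be included in the phase II portion of the study". The lead-in is capped: "Up to 24 patients will be accrued into lead-in part of the study". Once the MTD is judged safe, "any patients still on study at a dose lower than MTD can be dose escalated up to MTD".
- Section 5.2.1.4: the lead-in begins with 6 patients at level -1. "The dose adjustment (Table 1) will continue in cohorts of 6 until we reach a dose level at which" fewer than 2 of 6 have a DLT. That level "will be the MTD and will be used to treat an additional 34 patients in the phase II portion of the study". Section 5.2.1.5 replaces patients who leave before day 28 without a DLT and for reasons other than toxicity.
- Section 5.4.2: a patient needs one full course (seven days of 5-azacytidine and one lirilumab dose) to count as adequately treated for efficacy. A single dose of either drug suffices for toxicity.

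**The concern.** The phase II question is whether the regimen at the selected dose reaches an ORR of 30%, against 10-15% historically. Section 11.1 implies a denominator of 40 patients, all treated at that dose. Section 11.2, followed as written, adds the lead-in patients treated at other levels, so the reported ORR would mix dose levels and its n would differ from the 40 at which the monitoring in Tables 4 and 5 ends.

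The escalation rule adds a second uncertainty. A lead-in patient who started below the MTD and was later moved up might or might not be regarded as treated at the MTD. Only patients still on study can be moved up, so counting them would favour those who had done well enough to stay.

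The trial is single-arm and open-label. If the denominator is left open, it can be settled after responses are known.

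**Working it through.** **Inputs.** Cohorts of 6, starting at level -1 (sections 5.2.1.1 and 5.2.1.4); five levels listed, -4 to 0 (Table 1); lead-in cap 24 and phase II n of 40 (section 11.1); 34 further patients at the MTD (section 5.2.1.4); target ORR 30% (section 11.2).

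**The plan's own counts.** The longest lead-in path is -1, -2, -3, -4, giving 4 × 6 = 24. Phase II is 6 + 34 = 40. Both stated figures reproduce.

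**Patients at other levels, path by path.** With 0 or 1 DLT in 6 at level -1, level 0 opens; with 2 or more, level -2 opens. A second cohort is therefore always treated. Counting 34 new patients plus everyone in the lead-in, before any replacements:

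| MTD | Levels treated in lead-in | Off-MTD patients | Literal denominator | Off-MTD patients relative to MTD |
|---|---|---|---|---|
| 0 | -1, 0 | 6 | 46 | below |
| -1 | -1, 0 | 6 | 46 | above |
| -2 | -1, -2 | 6 | 46 | above |
| -3 | -1, -2, -3 | 12 | 52 | above |
| -4 | -1, -2, -3, -4 | 18 | 58 | above |

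No path gives 40, and no path uses more than four levels.

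**How likely each count is.** The documents give no DLT rates, so assume one common rate p at every level. A cohort fails with probability f = 1 − (1−p)^6 − 6p(1−p)^5. The 18-patient path has probability f³(1−f). The three 6-patient paths together have (1−f)² + (1−f)f + f(1−f).

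| Assumed p | 6 off-MTD | 18 off-MTD |
|---|---|---|
| 10% | 98.7% | 0.1% |
| 20% | 88.1% | 2.7% |
| 30% | 66.4% | 8.2% |
| 40% | 41.2% | 10.5% |

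The remainder is the 12-patient path, or no MTD found.

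**Effect on the ORR.** Assume 30% at the MTD (12/40) and a rate q in the k other patients, with q from 10% to 45%. The expected pooled ORR is (12 + kq)/(40 + k).

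- k = 6: 12.6/46 = 27.4% to 14.7/46 = 32.0%.
- k = 12: 13.2/52 = 25.4% to 17.4/52 = 33.5%.
- k = 18: 13.8/58 = 23.8% to 20.1/58 = 34.7%.

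The exact (Clopper-Pearson) 95% interval for 12/40 is 16.6% to 46.5%.

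**Crossing the target.** With 12/40 = 30.0% at the MTD, adding 1 responder among 6 gives 13/46 = 28.3%. With 11/40 = 27.5%, adding 3 among 6 gives 14/46 = 30.4%.

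**The case against.** The strongest reply is that the specific text already points to 40. ORR is the Part b objective, section 11.1 names only MTD patients for carry-over and fixes their number at 6, and the monitoring tables end at 40. On this view the sentence in section 11.2 is only an evaluability rule: dosed patients are not excluded, and drop-outs count as failures. Patients escalated later were not treated at the MTD during the lead-in, so they stay out.

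Much of this stands. A reader might infer from section 11.2 that up to 18 off-MTD patients will certainly be pooled into the primary ORR. The documents do not support that, because section 11.1 supports the narrower set; what they contain is an unresolved conflict. A reader might also infer that pooling dilutes the ORR. That is not supported either: the other patients are below the MTD only if the MTD is level 0, and above it on every other path.

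The reply does not remove the conflict. The same sentence defines the safety set, so reading it as phase II only would drop off-MTD lead-in patients from the safety analysis, although safety is the lead-in's stated objective. As an evaluability rule it still disagrees with section 5.4.2. It is true that no formal final test depends on the set and that the stopping boundaries are unaffected, but the estimate to be judged against 30% is affected.

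**Conclusion.** The concern holds as a conflict between section 11.2 and sections 11.1 and 5.2.1.4 over the primary ORR denominator, with section 5.4.2 adding a third rule. Read literally, section 11.2 brings in at least 6 off-MTD patients on every path that reaches an MTD; 18 is a ceiling reached only if levels -1, -2 and -3 all fail and -4 passes. In the 6-patient case the expected shift is at most about 2.6 percentage points under the assumed rates, which is minor beside the sampling uncertainty but enough to change which side of 30% the estimate falls on. The case for correction rests more on an undefined primary denominator in an open-label trial than on the size of the bias. The response rates at other levels and the common DLT rate are assumptions; the patient counts follow from the documents.

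**What to change.** In section 11.2, state that the primary ORR set is all patients whose first study dose was at the level selected as the MTD: planned 6 + 34 = 40. Say that patients dosed at that level and later replaced are counted, so n may slightly exceed 40. Report lead-in patients who started at other levels, including those later escalated, separately by starting level. Keep the any-dose rule for the safety set. Reconcile section 5.4.2 by saying whether the one-full-course rule has any role in the primary ORR or only defines a supportive analysis.

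The cost is a short text amendment to sections 11.2 and 5.4.2, with no added patients, visits or procedures, and it should be made before responses are summarised.

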1.0 OBJECTIVES

1.1 Primary Objectives

Part a. Lead-in phase:

1. To determine the maximum tolerated dose (MTD) and dose limiting toxicity (DLT) of lirilumab in combination with 5-azacytidine in patients with refractory/ relapsed (AML).

Part b. Phase II:

1. To determine the overall response rate (ORR) of lirilumab in combination with 5-azacytidine in patients with refractory/ relapsed AML.

1.2 Secondary Objectives:

1. To determine the duration of response, disease-free survival (DFS), and overall survival (OS) of patients with refractory/ relapsed AML treated with this combination.
2. To determine the safety of lirilumab in combination with 5-azacytidine in patients with refractory/ relapsed AML.

1.3 Exploratory Objectives:

1. To study immunological and molecular changes in the peripheral blood and bone marrow in response to lirilumab and 5-azacytidine therapy.
2. To determine induction of hypomethylation and DNA damage during therapy with this combination and its correlation with response.

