If prolonged myelosuppression (more than 8 weeks) WITH evidence of a hypocellular marrow (marrow cellularity less than 5% without evidence of leukemia) is observed, 5-azacytidine and lirilumab will be discontinued. Delays in start of subsequent cycles greater than 8 weeks will be acceptable only for patients who are deriving clinical benefit and after discussion with the principal investigator of potential risk/benefit ratio. If the peripheral counts do not recover (ANC $<1 \times 10^9/L$ and/or platelets $<30 \times 10^9/L$) but there is evidence of residual leukemia in the bone marrow, subsequent cycles can be administered at the discretion of the treating physician not earlier than 21 days after the prior cycle.

5.2.2.4 For patients who discontinue therapy, the reason for treatment discontinuation will be captured.

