5.4 Duration of Therapy

In the absence of treatment delays due to adverse events, treatment may continue until one of the following criteria applies:

1. Clinically significant progressive disease, or
2. Intercurrent illness that prevents further administration of treatment, or
3. Patient request, or
4. General or specific changes in the patient's condition render the patient unacceptable for further treatment in the judgment of the investigator, or
5. Unacceptable toxicity that in the opinion of the investigator makes it unsafe to continue therapy.
 - 5.4.1 It is planned that up to a total of 24 cycles of therapy will be administered for patients deriving benefit from this regimen. Continuation of therapy for patients completing 24 cycles of therapy may be considered on a case-by-case basis after discussion with the principal investigator.
 - 5.4.2. A minimum of 1 full course (defined as the administration of 5-azacytidine for 7 days and one dose of lirilumab) will be required for a patient to be considered as having received an adequate trial to evaluate efficacy. All patients receiving at least one dose of any of the two drugs will be considered evaluable for toxicity.

5.5 Supportive Care:

Supportive care measures including blood products, infection prophylaxis and growth factors will be administered according to institutional and Leukemia Department guidelines.

Supportive care measures including blood products, infection prophylaxis and growth factors will be administered according to institutional and Leukemia Department guidelines.

Management Algorithms for Treatment of Lirilumab Related Adverse Events

Immuno-oncology (I-O) agents are associated with AEs that can differ in severity and duration than AEs caused by other therapeutic classes. Lirilumab is considered an immuno-oncology agent in this protocol. Early recognition and management of AEs associated with immuno-oncology agents such as lirilumab may mitigate severe toxicity. Lirilumab has a known safety profile however, a general principle is that differential diagnoses should be diligently evaluated according to standard medical practice. Non-inflammatory etiologies should be considered and appropriately treated. Corticosteroids are a primary therapy for immuno-oncology drug-related adverse events, and lirilumab is no exception. The oral equivalent of the recommended IV doses may be considered for

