 2. A letter to the local physician outlining the patient's participation in a clinical trial will request local physician agreement to supervise the patient's care (Appendix H)
 3. Protocol required evaluations outside MDACC will be documented by telephone, fax or e-mail. Fax and/or e-mail will be dated and signed by the MDACC physician, indicating that they have reviewed it. Changes in drug dose and/or schedule must be discussed with and approved by the MDACC physician investigator, or their representative prior to initiation, and will be documented in the patient record.
 4. A copy of the informed consent, protocol abstract, treatment schema and evaluation during treatment will be provided to the local physician.
 5. Documentation to be provided by the local physician will include progress notes, reports of protocol required laboratory and diagnostic studies and documentation of any hospitalizations.
 6. The home physician will be requested to report to the MDACC physician investigator all life threatening events within 24 hours of documented occurrence.
 7. All follow-up visits will be performed at MDACC. Patients will return to MDACC for physical examination at the start of each cycle i.e. approximately every 28 days (+/-7).
- 7.2.10 End of Treatment Visit to be completed 30 days (+/-7 days) after the last dose of study drug. Blood (about 2-3 teaspoons) will be drawn for CBC, platelet count, differential, creatinine, total bilirubin, ALT. No other procedures or labs will be needed.
- 7.2.11 Patients with an objective response at completion of active study treatment will be followed for survival at MD Anderson Cancer Center (MDACC) for up to 90 days after completion of active treatment and while still on study. If the patient is unable to return to MDACC the follow-up visits may be conducted via telephone.

Data regarding adverse events will be collected during the study. Please see **Appendix D** regarding data capturing of adverse events and adverse events source documentation. Protocol specific data will be entered into PDMS/CORE. PDMS/CORE will be used as the electronic case report form for this protocol. Only unexpected AEs will be recorded in the Case Report Form (CRF). The Principal Investigator will sign and date the AE log per each

patient at the completion of each course. Following signature, the AE log will be used as source documentation for the adverse events for attribution.

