9.1.4 Follow-Up at Treatment Discontinuation or Early Withdrawal

Patients who discontinue treatment for any reason should complete end-of-treatment procedures when possible. End of treatment procedures will include a physical examination, CBC with differential and platelets and a limited chemistry profile (total bilirubin, serum creatinine, SGPT or SGOT). A bone marrow aspiration may be recommended only if non-response or progressive disease cannot be unequivocally diagnosed from peripheral blood. Although treatment will be discontinued at that time, all patients who do not withdraw consent for follow-up, die, or become lost to follow-up, will remain on study for follow-up evaluations. Subject will be followed for toxicity for at least 30 days after the last protocol treatment. The 30-day follow-up visit will be scheduled as a clinic visits for clinical evaluation and physical examinations. If the patient cannot make it to the MDACC clinic for this visit, the required follow up treatment procedures may be done with a local physician and the records forwarded to MDACC. The research nurse will contact the patient by telephone and get a verbal assessment of the patient's condition. The phone conversation will then be documented in the patient's charts.

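### Section 11.2 summarises duration of response by mean, SD, median and range, not by Kaplan-Meier, and gives no rule for responses still ongoing

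*Combined protocol and SAP*

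**What the plan says.** Section 1.2 gives the first secondary objective: "To determine the duration of response, disease-free survival (DFS), and overall survival (OS) of patients with refractory/ relapsed AML treated with this combination". Section 11.2 then treats these endpoints differently. Duration of response is placed with demographic and clinical characteristics: "including duration of response) and safety data of the patients will be summarized using descriptive statistics such as mean, standard deviation, median and range". In the next paragraph the time-to-event endpoints, first given as DFS and OS, are described as "including overall survival and progression free survival will be estimated using the method of Kaplan and Meier". Duration of response is not named there. The plan defines neither its start nor its end, and has no censoring rule for it.

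Several places foresee patients who stop while still in response:
- Section 5.4.1: "It is planned that up to a total of 24 cycles of therapy will be administered for patients deriving benefit from this regimen".
- Section 5.4 allows stopping for intercurrent illness, patient request, or "Unacceptable toxicity that in the opinion of the investigator makes it unsafe to continue therapy".
- Section 5.2.2.4, on prolonged myelosuppression with a hypocellular marrow: "without evidence of leukemia) is observed, 5-azacytidine and lirilumab will be discontinued".
- Section 7.2.11: "Patients with an objective response at completion of active study treatment will be followed for survival at MD Anderson Cancer Center", for up to 90 days.

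After treatment, section 7.2.10 schedules a blood count with differential at 30 days. Section 9.1.4 adds a clinic visit with physical examination, and on the marrow says: "A bone marrow aspiration may be recommended only if non-response or progressive disease cannot be unequivocally diagnosed from peripheral blood". Section 9.1.4 also keeps all patients on study for follow-up unless they withdraw consent, die or are lost. It names no survival contact and no data cutoff.

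**The concern.** A response that has not ended has a known minimum length and an unknown final length. A mean, SD or range cannot carry that information, so someone must decide whether such a response counts as ended at last assessment or is left out. Section 11.2 does not say which, and the choice could be made after the data are seen.

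Duration of response tells a reader whether responses last. In a single-arm trial it will be set beside history, and section 2.2 quotes a median of 9 months for salvage therapy. A shortened estimate would distort that comparison.

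A smaller, related matter is survival follow-up. Sections 7.2.11 and 9.1.4 describe different populations and durations, and the overall survival estimate depends on which one governs.

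**Working it through.** The plan states no figure for duration of response, so there is nothing to reproduce. The size below is an illustration.

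**Inputs**
- True median 9 months (section 2.2); exponential shape assumed. Rate λ = ln 2 / 9 = 0.0770; true mean = 9 / ln 2 = 13.0 months.
- 24 cycles × 28 days = 22.1 months on treatment (section 5.4.1). Response at 1.5 months is assumed, leaving D = 22.1 − 1.5 = 20.6 months in response.
- Other stops while in response (assumed, independent of relapse): none, median 24 months (μ = 0.0289), or median 12 months (μ = 0.0578).
- Last disease assessment taken at the stop.

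**Formulas**, with r = λ + μ and q = exp(−rD)
- Share ongoing = 1 − (λ/r)(1 − q)
- Mean, ongoing counted as ended = (1 − q)/r
- Median, ongoing counted as ended = ln 2 / r (valid because q < 0.5)
- Median of completed responses only = −ln((1 + q)/2)/r

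| Other stops | r | q | Ongoing | Mean | Median | Median, completed only |
|---|---|---|---|---|---|---|
| None | 0.0770 | 0.205 | about 20% | 0.795/0.0770 = 10.3 | 9.0 | 6.6 |
| Median 24 mo | 0.1059 | 0.113 | about 35% | 0.887/0.1059 = 8.4 | 6.5 | 5.5 |
| Median 12 mo | 0.1348 | 0.062 | about 46% | 0.938/0.1348 = 7.0 | 5.1 | 4.7 |

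The truth is a mean of 13.0 and a median of 9.0. In a very large sample the Kaplan-Meier median is 9.0 in all three rows.

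**Other true medians, same formulas.** With a true median of 6 (mean 8.7), the mean is 7.9, 6.6 and 5.6 and the median 6.0, 4.8 and 4.0. With a true median of 12 (mean 17.3), the mean is 12.0, 9.6 and 7.9 and the median 12.0, 8.0 and 6.0.

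**At the size of this trial.** The target response rate of 30% in 40 patients gives 0.30 × 40 = 12 responders. Simulating 12 responders at a true median of 9:
- The plain median falls below 9 in 49%, 79% and 94% of trials across the three rows; the Kaplan-Meier median does so in 61%, 52% and 50%.
- The median absolute error is about 2.3, 2.7 and 3.8 months for the plain median, against about 2.5, 2.8 and 2.9 for Kaplan-Meier.

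A second simulation used uniform administrative censoring at 3–12, 6–18 or 12–24 months (58%, 41% and 26% ongoing). The raw mean was 5.5, 7.6 and 9.6, and the Kaplan-Meier median was not reached in 40%, 11% and 1% of trials.

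**Survival follow-up.** Section 7.2.11 covers patients in response at completion, for up to 90 days. Section 9.1.4 covers everyone who has not withdrawn, died or been lost, with a 30-day minimum that concerns toxicity. If 9.1.4 means that vital status is followed for all, overall survival is estimated without this bias.

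The narrower reading is that last contact comes 30 days after treatment ends. It was simulated with 30% responders (median survival 12 months, assumed) and non-responders at 3.8 months. That last figure comes from section 2.2, where it describes a whole refractory group. True 12-month survival is 23%. Kaplan-Meier gives 37%, 34%, 31% and 31% when non-responders stop after 1–3, 2–4, 2–6 or 3–6 cycles, an excess of 37 − 23 = 14 down to 31 − 23 = 8 points. Adding the 90-day responder clause moves these by about 1 point at most. With 40 patients the standard error under this follow-up is 12–15 points, because only about 2 patients remain at risk at 12 months. The uncensored binomial value, √(0.229 × 0.771/40) = 6.6 points, does not apply.

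**The case against.** The strongest reply is that section 11.2 is underspecified, not wrong. Both lists are open: the descriptive statistics are given as examples, and the Kaplan-Meier sentence says it includes certain endpoints without claiming to be complete. Nothing states that ongoing responses will be counted as ended or dropped. This stands as far as it goes: the plan does not forbid Kaplan-Meier. But it names duration of response in one list and not in the other, and a mean and SD of censored times have no valid reading without a rule.

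A reader might infer four stronger claims that the documents do not support.
- **Every plain summary understates duration.** The plain median is unbiased when the only stop in response is the 24-cycle limit.
- **Kaplan-Meier would be much more accurate here.** With about 12 responders it is clearly better only in the heaviest censoring case; in the lightest it falls below the truth more often than the plain median.
- **No disease assessment exists after treatment.** There is a 30-day blood count and clinic visit, with a marrow when blood is not decisive. What is unspecified is assessment beyond that.
- **Overall survival is biased.** This requires reading 9.1.4 as ending contact soon after treatment, whereas its stated exits are withdrawal, death and loss to follow-up. Even then the excess is about one standard error or less.

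**Conclusion.** The point holds for duration of response. The plan assigns a censored secondary endpoint to statistics that cannot handle censoring and gives no rule for ongoing responses. If they are counted as ended, the mean is low by 13.0 − 10.3 = 2.7 up to 13.0 − 7.0 = 6.0 months in the illustration. The plain median ranges from correct to 9.0 − 5.1 = 3.9 months low. Dropping ongoing responses lowers the median by 2.4 to 4.3 months. These sizes rest on exponential durations, a 9-month median and assumed stopping rates independent of relapse; the direction for the mean does not depend on those particular values.

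The case for Kaplan-Meier is that it uses ongoing responses correctly and fixes their handling in advance, not that it will be precise with a dozen responders. On overall survival the finding is only that two sections need aligning. Both matters concern secondary estimates and leave the primary analysis and the monitoring boundaries as they are. It should be corrected, but it does not threaten the trial's main conclusion.

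**What to change.** In section 11.2, remove duration of response from the descriptive list. State that it is estimated by Kaplan-Meier among responders, from first response to relapse, progression or death, censored at the last disease assessment, with a 95% confidence interval for the median. The same sentence should say how transplant or a new therapy is handled. This is a wording change with no effect on sample size or visits. It does not lengthen disease assessment after treatment, so the number of responses still ongoing at last assessment should be reported with the estimate.

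Separately, align 7.2.11 with 9.1.4: vital status for every treated patient, whatever the response, until death or one common data cutoff, with overall survival censored at the date last known alive. The cost is a short amendment and periodic calls or record checks for at most 24 + 34 = 58 patients. Telephone contact already appears in both sections. A consent update may be needed; this cannot be checked because the consent pages are not in the supplied text.
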